### **3.2.3 Subject Restrictions During the Study**

#### **3.2.3.1 General and Dietary**

To avoid false positive drugs of abuse Screening results, subjects should refrain from food or drink containing poppy seeds (eg, specialty breads and muffins) for 72 hours before the screening visit.

#### **3.2.3.2 Contraception and Pregnancy Avoidance Procedures**

Female subjects **not** of childbearing potential must (defined as any female who has experienced menarche and who is NOT permanently sterile or post-menopausal) be post-menopausal (defined as amenorrhea for 12 consecutive months without an alternative medical cause or documented plasma follicle-stimulating hormone level in the post-menopausal range) or surgically sterile (ie, hysterectomy, bilateral tubal ligation, or bilateral oophorectomy). NOTE: these procedures and/or laboratory test results must be confirmed by physical examination or be provided through medical documentation. If of childbearing potential, female subjects must be practicing a medically approved and highly effective method of contraception (defined as those which result in a low failure rate [ie, less than 1% per year] when used consistently and correctly).

All female subjects of childbearing potential must have a negative pregnancy test at Screening and before dosing with study drug. Women of childbearing potential must agree to be heterosexually inactive from at least 21 days prior to enrollment and through 3 months after the final vaccination or agree to consistently use any of the following methods of contraception from at least 21 days prior to enrollment and through 3 months after the final vaccination: condoms (male or female) with spermicide, diaphragm with spermicide, cervical cap with spermicide, intrauterine device, oral or patch contraceptives, Norplant®, Depo-Provera®, or other FDA-approved contraceptive method that is designed to protect against pregnancy. Periodic abstinence (eg, calendar, ovulation, symptothermal, post-ovulation methods) and withdrawal are not acceptable methods of contraception.

Male subjects must use an acceptable method of birth control throughout the entire study (see above). Males must also agree to refrain from donation of sperm from the time of first vaccination until 3 months following the last vaccination. Periodic abstinence, declaration of abstinence for the duration of the study, and withdrawal are not acceptable methods of contraception.

Female subjects of childbearing potential and male subjects will be provided with information on acceptable methods of contraception as part of the subject informed consent process and will be asked to sign a consent form stating that they understand the requirements for avoidance of pregnancy.

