4. Female subjects must be non-pregnant and non-lactating and meet one of the following criteria: a) post-menopausal (defined as 12 consecutive months with no menses without an alternative medical cause or documented plasma follicle-stimulating hormone level in the post-menopausal range); b) surgically sterile (ie, hysterectomy, bilateral tubal ligation, or bilateral oophorectomy). NOTE: these procedures and laboratory test results must be confirmed by physical examination or official written confirmation of a procedure; c) if of childbearing potential (defined as any female who has experienced menarche and who is NOT permanently sterile or post-menopausal), agrees to be heterosexually inactive from at least 21 days prior to enrollment and through 3 months after the final vaccination or agrees to consistently use any of the following methods of contraception from at least 21 days prior to enrollment and through 3 months after the final vaccination: condoms (male or female) with spermicide, diaphragm with spermicide, cervical cap with spermicide, intrauterine device, oral or patch contraceptives, Norplant®, Depo-Provera®, or other Food and Drug Administration (FDA)-approved contraceptive method that is designed to protect against pregnancy. Periodic abstinence (eg, calendar, ovulation, symptothermal, post-ovulation methods) and withdrawal are not acceptable methods of contraception. Male subjects must use an acceptable method of birth control (see above) and must also agree to refrain from donation of sperm from the time of first vaccination until 3 months following the last vaccination. Periodic abstinence, declaration of abstinence for the duration of the study, and withdrawal are not acceptable methods of contraception.
5. Subject assigned to the flavivirus seropositive group has received a yellow fever vaccination in the past 20 years by either: a) military assignment in the previous 20 years that requires a yellow fever

vaccination; or 2) yellow fever vaccination documented on an international certificate or other confirmatory documentation.

6. The subject understands and agrees to comply with the study procedures and provides written informed consent.
7. The subject has access to a consistent and reliable means of telephone contact, which may be in the home, workplace, or by personal mobile electronic device.

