### **3.2.1 Inclusion Criteria**

Each subject must meet all of the following criteria during the screening period to be enrolled in this study:

1. The subject is male or female between 18 and 49 years of age, inclusive.
2. The subject has a body mass index between 18 and 35 kg/m^2, inclusive.
3. The subject is considered by the investigator to be in good general health as determined by medical history.
4. Female subjects must be non-pregnant and non-lactating and meet one of the following criteria: a) post-menopausal (defined as 12 consecutive months with no menses without an

alternative medical cause or documented plasma follicle-stimulating hormone level in the post-menopausal range); b) surgically sterile (ie, hysterectomy, bilateral tubal ligation, or bilateral oophorectomy). NOTE: these procedures and laboratory test results must be confirmed by physical examination or official written confirmation of a procedure; c) if of childbearing potential (defined as any female who has experienced menarche and who is NOT permanently sterile or post-menopausal), agrees to be heterosexually inactive from at least 21 days prior to enrollment and through 3 months after the final vaccination or agrees to consistently use any of the following methods of contraception from at least 21 days prior to enrollment and through 3 months after the final vaccination: condoms (male or female) with spermicide, diaphragm with spermicide, cervical cap with spermicide, intrauterine device, oral or patch contraceptives, Norplant®, Depo-Provera®, or other FDA-approved contraceptive method that is designed to protect against pregnancy. Periodic abstinence (eg, calendar, ovulation, symptothermal, post-ovulation methods) and withdrawal are not acceptable methods of contraception. Male subjects must use an acceptable method of birth control (see above) and must also agree to refrain from donation of sperm from the time of first vaccination until 3 months following the last vaccination. Periodic abstinence, declaration of abstinence for the duration of the study, and withdrawal are not acceptable methods of contraception.

5. Subject assigned to the flavivirus-seropositive group has received a yellow fever vaccination in the past 20 years by either: a) military assignment in the previous 20 years that requires a yellow fever vaccination; or 2) yellow fever vaccination documented on an international certificate or other confirmatory documentation.

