Childbearing potential defined as any female who has experienced menarche and who is NOT permanently sterile or post-menopausal. Post-menopausal is defined as 12 consecutive months with no menses without an alternative medical cause.

Note: X/Xc denotes being performed before and after vaccination.

- a Visit 3a will comprise of sentinel cohort only.
- b To confirm post-menopausal status, as needed.
- c Serology testing will include hepatitis B surface antigen, hepatitis C virus antibody, and human immunodeficiency virus type 1 and 2 antibodies.
- d At Screening, if the subject has no proof of yellow fever vaccination within 20 years, or other documentation of flavivirus status, the West Nile virus screening test will be administered. West Nile virus serology screen can occur up to 90 days prior to randomization.
- e Urine drug screen for drugs of abuse will be performed at Screening and before dose administration at Visit 1 for opiates, cocaine, phencyclidine, amphetamines, benzodiazepines, and methadone (cannabis excluded).
- f Full physical examination at Screening; symptom-directed (targeted) physical examination at all other scheduled time points. Interim physical examinations will be performed at the discretion of the investigator, if necessary. Height and weight will be measured and body mass index calculated at Screening only.
- g Vital sign measurements (systolic and diastolic blood pressures, heart rate, respiratory rate, and body temperature) at Visit 1 and Visit 4 will be collected once before dose administration and at least 60 minutes after dose administration (before subjects are discharged).
- h Safety laboratory test values include hematocrit, hemoglobin, mean corpuscular hemoglobin, mean corpuscular hemoglobin concentration, mean corpuscular volume, platelet count, red blood cell count, total and differential white blood cell count, alanine aminotransferase, alkaline phosphatase, aspartate aminotransferase, amylase, lipase, bilirubin (total and direct), blood urea nitrogen, creatinine, random glucose, potassium, sodium, total protein, calcium, albumin, prothrombin time, partial thromboplastin time.
- i A subset of safety laboratory test values for albumin, bilirubin (total and direct), prothrombin time, partial thromboplastin time, alkaline phosphatase, alanine aminotransferase, aspartate aminotransferase.

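### Section 3.2.3.2 gives women of childbearing potential two contraception rules, and inclusion criterion 4 carries only the one without a failure-rate limit; a lesser mismatch is that the Table 6-1 note omits FSH from its definition of post-menopausal

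*Protocol*

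**What the plan says.** **Contraception.** Section 3.2.3.2 of the protocol addresses women of childbearing potential twice. The first paragraph requires a "highly effective method of contraception (defined as those which result in a low failure rate [ie, less than 1% per year", judged under consistent and correct use. It offers no abstinence option. The second paragraph starts from a different alternative: "Women of childbearing potential must agree to be heterosexually inactive from at least 21 days prior to enrollment". Women who are not inactive may instead use any method on a list of barrier methods with spermicide, an intrauterine device and hormonal methods, closing with "or other FDA-approved contraceptive method that is designed to protect against pregnancy". No failure-rate limit is attached to that list.

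Inclusion criterion 4 (Section 3.2.1, repeated in the synopsis) opens with "Female subjects must be non-pregnant and non-lactating and meet one of the following criteria". For women of childbearing potential it then asks that the subject "agrees to be heterosexually inactive from at least 21 days prior to enrollment and through 3 months after the final vaccination" or use a method from the same open list. It has no failure-rate limit.

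**Post-menopausal status.** Criterion 4 counts a woman as post-menopausal after 12 months without menses and no "alternative medical cause or documented plasma follicle-stimulating hormone level in the post-menopausal range", so FSH is a separate route. The synopsis version has the same alternative ("documented plasma follicle-stimulating hormone level in the post-menopausal range"), and so does Section 3.2.3.2. The notes to Table 6-1 give only the first route: "Post-menopausal is defined as 12 consecutive months with no menses without an alternative medical cause". Section 3.5.8 and Table 6-1 (including note k) schedule pregnancy tests for women of childbearing potential only, at Screening and before each dose.

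**The concern.** Sites screen on the inclusion criteria. A site applying criterion 4 makes no below-1% check, while Section 3.2.3.2 requires one. Section 3.2.3.2 also asks subjects to sign that they understand the pregnancy-avoidance requirements, and they cannot be told one clear requirement while two are in force.

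This is operative safety text. Section 1.3 reports no clinical studies of mRNA-1325, and Section 1.2.4 describes the rat developmental and reproductive toxicology study as proposed only. Avoiding pregnancy is therefore a working safeguard in this trial.

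The second mismatch matters less. It decides whether a particular woman has scheduled pregnancy tests. It does not decide whether pregnancy bars her from entry.

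**Working it through.** The protocol gives no figure to reproduce for the contraception conflict, so the check sets the texts side by side.

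**Step 1: the contraception rules.** Section 3.2.3.2 contains one failure-rate limit and criterion 4 contains none. Three kinds of candidate show the effect:

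| Candidate | Criterion 4 | 3.2.3.2, second paragraph | 3.2.3.2, first paragraph |
|---|---|---|---|
| Heterosexually inactive, no method | Met | Met | Not met if read literally |
| Listed method that meets the below-1% standard | Met | Met | Met |
| Method within the open list, below-1% standard not shown | Met | Met | Not met, or cannot be determined |

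The texts agree only in the second row.

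**Step 2: a cumulative reading.** Suppose the two paragraphs of Section 3.2.3.2 apply together, so that a method must be on the list and also meet the limit. Criterion 4 still lacks the limit. A candidate in the third row passes eligibility and can breach Section 3.2.3.2.

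**Step 3: scheduled pregnancy tests.** Take a woman who is not surgically sterile, has a post-menopausal FSH value and has had less than 12 months without menses.

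- Under criterion 4 and Section 3.2.3.2 she is post-menopausal and so not of childbearing potential: 0 scheduled tests.
- Under the Table 6-1 note read alone she is of childbearing potential: 1 at Screening + 1 before dose 1 (Visit 1) + 1 before dose 2 (Visit 4) = 3 scheduled tests.

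Exclusion criterion 3 and the negative-test requirement in Section 3.2.3.2 are also limited to women of childbearing potential, so they turn on the same definition.

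**The case against.** **On contraception.** The best defence is that Section 3.2.3.2 sets a general standard and then lists methods, that subjects must meet both the inclusion criteria and the study restrictions, and that the stricter sentence governs. On that view criterion 4 merely fails to repeat it. This is a possible reading, but it leaves eligibility and restriction out of step, and it does not supply the inactivity option that the first paragraph lacks.

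A reader might infer that the barrier methods on the list fail the below-1% standard and that the plan therefore admits extra pregnancies. The documents give no failure rates and do not support that. Nor can the 1% figure be prorated into a cap on risk during the trial. It applies only under consistent and correct use. The time at risk also has no firm upper bound, because Section 3.4.2.2 suspends the second-dose window during a pause and Section 3.4.7 treats a vaccination as missed only when it is more than 28 days late.

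**On FSH.** Table 6-1 has its own FSH row, and its note b and Section 3.5.8 use FSH to confirm post-menopausal status. Read with these, the intended answer is probably 0 scheduled tests, and the figure of 3 comes only from the short note taken alone. That objection largely stands. What remains is a definition that omits a route stated in three other places.

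A reader might also infer that a pregnant woman could be enrolled through the FSH route. Criterion 4 requires every female subject to be non-pregnant, unscheduled serum tests are allowed as needed, and pregnancy reporting (Section 3.5.7.1.4) and the option to withhold vaccination (Section 3.3.1) are not limited to childbearing potential.

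**Conclusion.** The contraception conflict holds and should be corrected. Section 3.2.3.2 states two rules, criterion 4 carries only the one without a limit, and a woman can satisfy criterion 4 while breaching Section 3.2.3.2. This follows from the wording alone. Its size in pregnancies cannot be computed from the documents, and no excess is claimed.

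The FSH mismatch is real but minor: 0 or 3 scheduled tests for a woman qualifying on FSH alone, with the 3 resting on the table note read in isolation. The number of such women is not given. I assume it is small, since the upper age limit is 49.

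Neither point affects an endpoint, an analysis or a dose decision.

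**What to change.** 1. **Contraception.** Put one identical rule in criterion 4 (synopsis and Section 3.2.1), Section 3.2.3.2 and the consent text. Women of childbearing potential are either heterosexually inactive or use a listed method that meets the below-1% standard under consistent and correct use, from at least 21 days before enrollment through 3 months after the final vaccination. Name the qualifying methods. Without names, each site would have to judge which listed methods meet the standard, and the protocol gives it no rates to do so.
2. **Post-menopausal definition.** Add the FSH alternative to the Table 6-1 note so that it matches criterion 4 and Section 3.2.3.2.
3. **Optional precaution.** Completing the note alone settles the answer at 0 scheduled tests for a woman qualifying on FSH alone. The sponsor could also schedule tests for her at Screening and before each dose, by adding her to Section 3.5.8, the Table 6-1 pregnancy-test row and note k. This goes beyond removing the inconsistency.

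The cost is a wording amendment with matching consent text, possibly a few candidates changing method, and, if the option is taken, 3 scheduled tests for each woman concerned. Nobody loses eligibility through the FSH change.

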### **3.3 Withdrawal of Subjects From the Study**

#### **3.3.1 Reasons for Withdrawal**

Subjects can withdraw consent and discontinue from the study at any time, for any reason, without prejudice to further treatment.

The investigator can also withdraw a subject, upon the request of Moderna Therapeutics, Inc. or if Moderna Therapeutics, Inc. terminates the study. Upon occurrence of a serious or intolerable AE, the investigator will confer with the Sponsor or designee. If a subject desires to withdraw from the study because of an AE, the investigator will try to obtain agreement to continue to follow that subject for that event only until it is resolved or until stable and then complete an EOS form. In the event of a safety concern that results in withholding from further vaccination, the subject will be continued in the trial for safety evaluations.

Every reasonable attempt will be made to follow subjects for safety throughout the entire trial period even if further vaccination is withheld or the subject misses visits. The reason for subject withdrawal or lost to follow-up will be documented.

The investigator, in consultation with the Sponsor's medical monitor, **may** withhold a subject **from further vaccination** if the subject experiences any of the following:

1. Becomes pregnant;
2. Develops, during the course of the study, symptoms or conditions listed in the exclusion criteria;

3. Experiences an AE (other than reactogenicity) after vaccination that is considered by the investigator to be possibly or probably related to treatment and is of Grade 3 (severe) or higher severity;
4. Experiences an AE or SAE that, in the judgment of the investigator, requires study drug withdrawal due to its nature, severity, or required treatment, regardless of the causal relationship to treatment;
5. Experiences a clinically significant change in clinical laboratory test results, vital signs, or general condition that, in the judgment of the investigator, requires treatment withdrawal;
6. Experiences anaphylaxis clearly attributed to study vaccine;
7. Experiences generalized urticaria related to the study vaccine.

The reason for withdrawing or refusing from further vaccination will be recorded. In addition, if a subject refused further vaccination they will be continued in the trial with all planned visits and assessments relative to the vaccination schedule and including visits through 1 year post final vaccination.

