### **3.3.2 Handling of Withdrawals**

When a subject withdraws from the study, the reason(s) for withdrawal will be recorded by the investigator on the relevant page of the eCRF. These subjects will also be requested to complete all Visit 7 assessments. Any subject who fails to return for final assessments will be contacted by the site with a minimum of 3 phone call attempts, followed by a certified letter. After this final attempt the subject will be declared “lost to follow-up” on the EOS.

Lost to follow-up is defined by the inability to reach the subject after a minimum of 3 documented phone calls, faxes, text messages, or emails as well as lack of response by subject to 1 registered mail letter. All attempts should be documented in the subject’s source documents.

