### **3.5.7.1.3 Adverse Events of Special Interest**

Certain AESIs are evaluated after the administration of immunostimulatory agents. All subjects enrolled in the study will be monitored for AESIs from enrollment through the end-of-study (EOS) visit. The occurrence of any of these AEs will be treated as an SAE, meeting the criterion of a “medically important event.”

The list of AESIs is presented in [Section 6.2](#).

A diagnosis of an AESI will be reported to the Sponsor in an expedited manner similar to an SAE. The AESI diagnosis, as well as any medications taken to treat the condition, will be recorded in the subject’s eCRF.

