**Part B:**

- AESIs and SAEs through 1 year (or until resolved, whichever occurs first) following the last vaccination

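### A subject who leaves the study because of an AE is not asked to keep the one-year SAE/AESI safety contacts, and Sections 3.3.1 and 3.3.2 disagree on what is asked

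*Protocol*

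**What the plan says.** Section 3.3.1 separates stopping vaccination from leaving the study.

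- **Vaccination withheld:** "In the event of a safety concern that results in withholding from further vaccination, the subject will be continued in the trial for safety evaluations".
- **Further vaccination refused:** the subject stays in, with all planned visits up to one year after the final vaccination.
- **General rule:** "Every reasonable attempt will be made to follow subjects for safety throughout the entire trial period even if further vaccination is withheld", and the same applies when visits are missed.
- **Leaving the study:** the clause that opens "If a subject desires to withdraw from the study because of an AE" asks less. It says that "the investigator will try to obtain agreement to continue to follow that subject for that event only until it is resolved or until stable", and an EOS form is then completed.

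Section 3.3.2 says of withdrawing subjects generally: "These subjects will also be requested to complete all Visit 7 assessments". It asks for nothing after Visit 7.

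The safety targets run longer. Section 3.6.1 lists among the primary endpoints, for Part B, "AESIs and SAEs through 1 year (or until resolved, whichever occurs first) following the last vaccination". Section 3.5.7.1.3 states: "All subjects enrolled in the study will be monitored for AESIs from enrollment through the end-of-study (EOS) visit". Table 6-2 places the EOS visit at Visit 19.

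Section 3.6.4 puts everyone given at least one dose in the Safety set. Section 3.6.5.2 compares AEs as differences in proportions of subjects, each dose level against pooled placebo.

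**The concern.** The request to an AE leaver is limited to one event, and the EOS form then closes participation. Section 3.3.2 asks for more than that one event, so a site cannot follow both sections literally. Neither section asks for the monthly scripted contacts that collect SAEs and AESIs in Part B. For a subject who leaves during Part B, Visit 7 has already passed and Section 3.3.2 adds nothing.

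The comparator is saline, so exit because of an AE may be more frequent on vaccine. The leaver still counts in the Safety set, and an event arising after exit is no longer looked for. In a simple proportion that subject then counts as event-free for the rest of the year. If exit is unequal between groups in this direction, the vaccine-placebo difference in late SAEs and AESIs would be understated. The AESI list in Appendix 2 consists largely of immune-mediated disorders, which a year of contacts is meant to pick up.

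**Working it through.** **No plan figure to reproduce.** The protocol states no AE-withdrawal rate, dropout rate, SAE/AESI risk, alpha or power. Section 3.6.3 says that no formal sample size calculation was done. The group sizes are consistent: 3 × 30 = 90 subjects, 3 × 24 = 72 on vaccine and 3 × 6 = 18 on placebo, so 72:18 = 4:1.

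**Follow-up lost by one leaver.** The nominal window from first dose is 28 + 364 = 392 days, which matches Visit 19 in Table 6-2. If the event has settled by the exit day d, the share lost is (392 − d)/392:

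| Exit day d | Days lost | Share lost |
|---|---|---|
| 7 | 385 | 98% |
| 28 | 364 | 93% |
| 35 | 357 | 91% |
| 56 (Visit 7 completed) | 336 | 86% |

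Honouring the Visit 7 request therefore still leaves about 86% of the window uncovered. The denominator for that dose stays at 24; what is lost is observation time.

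**Effect on a group, by assumption.** Let w be the share of vaccine recipients who leave because of an AE (placebo taken as 0), r the SAE/AESI risk over 392 days, RR the relative risk in leavers, and t the day observation ends (14, or 56 if Visit 7 is completed). All four are assumptions.

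- Follow-up time lost in the vaccine group = w × (1 − t/392). For w = 2%, 5%, 10% and 20% this is 1.7–1.9%, 4.3–4.8%, 8.6–9.6% and 17–19%.
- Expected missed cases among 72 = 72 × w × r × RR × (1 − t/392).
- Understatement of the vaccine proportion = w × r × RR × (1 − t/392).

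With w = 5% (3.6 of 72 subjects) and r = 3%:

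- RR = 1: 72 × 0.05 × 0.03 × (0.857 to 0.964) = 0.09 to 0.10 cases, or 0.13 to 0.14 percentage points.
- RR = 3: 0.28 to 0.31 cases, or 0.39 to 0.43 points.

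Across w = 2–20%, r = 1–10% and RR = 1–3, the understatement runs from 0.02 points (0.02 × 0.01 × 1 × 0.857) to 5.8 points (0.20 × 0.10 × 3 × 0.964).

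**Against the imprecision.** The normal-approximation 95% half-width of a difference is 1.96 × √[p(1 − p)(1/n₁ + 1/18)]. This is rough at such small counts.

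| Risk p | 24 vs 18 | 72 vs 18 |
|---|---|---|
| 3% | 10.4 points | 8.8 points |
| 10% | 18.3 points | 15.5 points |

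At 5% withdrawal and 3% risk the understatement is well under one point, against about 10 points of imprecision.

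**The case against.** The strongest reply is that the subject's own exit shortens follow-up, not the clause. Section 3.3.1 gives every subject the right to leave at any time, and compared with a complete exit the clause asks for extra data. The protocol also has the main safeguard in place: subjects who react and stop vaccination stay under observation for the year. The AE that prompts withdrawal is itself recorded and listed. The comparison is descriptive, and the SAP may deal with incomplete follow-up.

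Much of this stands, and it rules out several stronger readings.

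- A reader might infer that follow-up is cut short in subjects who reacted. The text does not support that; only those who themselves choose to leave the study are affected.
- A reader might infer that sites are forbidden to ask for more. No sentence forbids it, and the general whole-trial rule points the other way. Sites are simply not told to ask.
- A reader might infer that each leaver removes 1/24, or 4.2%, of the dose group's denominator. Under the Safety set definition the denominator does not change.
- A reader might infer that leavers are the subjects most prone to a later immune-mediated event. Nothing in the protocol says so; RR = 3 above is only a sensitivity value.

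Two things do not fall. Wanting to stop clinic visits is not the same as refusing a telephone call, and no withdrawal path asks for the lesser commitment. And an SAP cannot recover events that nobody asked about, so this belongs in the protocol.

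**Conclusion.** The point holds as a gap and an inconsistency in a data-collection rule. Sections 3.3.1 and 3.3.2 ask different things of a subject who leaves because of an AE, and neither asks for the remaining SAE/AESI contacts that feed a primary safety endpoint.

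It would be tempting to conclude that the vaccine-placebo harm comparison is biased. The protocol supports only that it could be. That needs AE-driven exit to be more common on vaccine and late events to occur in those who left, and no rate is given for either. For the individual leaver the loss is large, 86% to 98% of the window. For the group it is small beside the imprecision unless withdrawal and event rates are both high. In a first-in-human study, though, a single unsought AESI could matter. The change is worth making because it is cheap and the missing data cannot be recovered later.

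**What to change.** Align the two sections.

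- In Section 3.3.1, replace the single-event limit with two requests: that any ongoing event be followed until resolved or stable, and that the subject accept the existing Part B scripted telephone SAE/AESI contacts through Visit 19, with no clinic visits or blood draws required. Complete the EOS form early only if the subject declines the contacts.
- In Section 3.3.2, state that the same requests apply to every withdrawing subject, whatever the reason and in every arm, alongside the Visit 7 request where that visit has not yet passed.

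The cost is about one sentence in each section, submitted as an amendment, and at most 12 short calls (Visits 8 to 19) per consenting subject. The script and contact schedule already exist (Section 3.5.1, Table 6-2). Refusal stays free, so some follow-up will still be lost; reporting follow-up time by treatment group would show how much.
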